8.0 FINANCIAL CONSIDERATIONS

Research subjects will not be paid for participation in this study. The cost of the MIBG and hospital stay will be covered by 3rd party payers. ¹³¹I-MIBG has been approved by the FDA for cost recovery. Stem cell harvest and infusion, outpatient visits, supportive care, MIBG scintigraphy and routine scans and laboratory monitoring will be billed in the usual manner, i.e. to third party payers.

9.0 POTENTIAL RISKS

¹³¹I-METAIODOBENZYLGUANIDINE (¹³¹I-MIBG)

Likely	Less Likely	Rare
(happens to 21-100 patients	(happens to 5-20 patients out	(happens to < 5 patients out every 100
out every 100 patients)	every 100 patients)	patients)
 Decrease in the number of red and white blood cells and platelets made in the bone marrow. You may need blood and platelet transfusions and usually stem cell infusions are necessary. The dose of 131 1-MIBG infusion used in this study may lower your blood counts. Lowering the number of red blood cells, which may make you tired or pale Nausea Dry mouth Alopecia (hair loss) High or low blood pressure during 1-MIBG infusion Loss of appetite 	 Fever or infection as a result of the low white blood cells. The infection may become serious. Fatigue from low red blood cells Not being able to get pregnant or have a child Decreased function of the thyroid gland. This causes tiredness (fatigue), weight gain, constipation, and lower blood pressure. Treatment for life with a medicine to supplement the thyroid gland (you.e. Synthroid or related thyroid supplement) may be needed. Respiratory or breathing problems 	 Pain and swelling in salivary glands Urinary tract infection from having a urinary catheter placed. (This is a risk from having a urinary catheter placed for 131 I-MIBG treatment not from the 131 I-MIBG itself.) Bruising or bleeding from the low platelet count. Bleeding can rarely become serious. Decreased function of adrenal gland. This affects your activity level and growth. It causes tiredness (fatigue), weight changes and blood pressure changes. You may need to take medicine to supplement the adrenal gland. Decreased heart function Irritation of the liver and/or kidneys. Because some of the radioactive I-MIBG is taken up by the liver and kidneys, there is a possible risk of future liver and/or kidney damage from the MIBG alone. Second cancer, different from the kind of cancer you have now (leukemia). Complications related to taking I-MIBG may result in death Dehydration Pain at tumor site Autonomic Neuropathy Blood Clots

POTASSIUM IODIDE (KI, SSKI)

Likely	Less Likely	Rare
(happens to 21-100 patients out of	(happens to 5-20 patients out of	(happens to <5 patients out of
every 100 patients)	every 100 patients)	every 100 patients)
	• Gastrointestinal distress (nausea / vomiting / diarrhea / stomach pain)	 Pain, tingling or weakness in arms and legs Vasculitis Flare-up of adolescent acne Irregular heartbeat Confusion Tiredness Fever Hypersensitivity (rash, hives) Burning of mouth / throat Metallic taste Rash Hypothyroidism Hyperthyroidism Swelling of lymph glands

POTASSIUM PERCHLORATE (KCLO4)

Likely	Less Likely	Rare
(happens to 21-100 patients out of	(happens to 5-20 patients out of	(happens to <5 patients out of
every 100 patients)	every 100 patients)	every 100 patients)
	 Gastrointestinal distress (nausea / vomiting / diarrhea / stomach pain) 	 Unable to make red and white blood cells, platelets Hypersensitivity (rash, hives)

In general, MIBG therapy has been well-tolerated by patients with pheochromocytoma and paraganglioma, many of whom have been heavily pretreated. The major risk for patients participating in this study is hematologic toxicity. The dose of MIBG chosen is expected to induce grade 4 hematopoietic toxicity in most patients. Thus, bleeding and/or infectious complications are possible and may be life threatening. Assuring hematopoietic stem cell availability, which may be used for hematopoietic "rescue," or administering the lower doses of ¹³¹I-MIBG when stem cells are not available, minimizes these risks. The risk of hypothyroidism is minimized by administration of a blocking agent during and for 6 weeks following MIBG therapy. There is a very small risk of radiation exposure to family members. Nausea, hypertension or hypotension are sometimes observed during ¹³¹I-MIBG infusion, but respond readily to treatment. Secondary leukemia or other malignancy is also a known but rare (<5%) risk of radiation, particularly in patients who have also received extensive prior

therapy. There is a theoretical risk from the radiation exposure to organs in which the ¹³¹I-MIBG concentrates, such as bladder, gonads, heart, lungs, and liver. The use of the Foley catheter effectively decreases the residence time of the radioactivity in the bladder to less than 5 minutes, thereby decreasing the bladder exposure to less than 300 cGy. There is still some controversy about the exposure to the liver and heart, areas of concentration of ¹³¹I-MIBG, but, to date, grade 3 or 4 hepatotoxicity has been <7% and cardiac and renal toxicity have not been reported. Lastly, patients with refractory malignant pheochromocytoma and paraganglioma may develop unexpected complications that may be life threatening.

10.0 POTENTIAL BENEFITS

It is possible that this therapy may relieve pain and/or decrease tumor burden. This may increase survival duration and potentially allow for additional MIBG or other experimental therapies. It is unlikely that MIBG therapy alone will cure any patient with refractory pheochromocytoma or paraganglioma. Successful completion of this clinical trial may benefit future patients with malignant pheochromocytoma or paraganglioma.

11.0 RISK/BENEFIT ANALYSIS

Patients who will be entering this trial will have a limited life expectancy. Based upon phase II and pilot data, this research study appears to have a reasonable chance of directly benefiting the research subject with a minimum of non-hematopoietic toxicity and average hospital days of fewer than 7. Thus, the potential benefits outweigh the potential risks.

12.0 PROTECTION OF SUBJECTS

Study generated data will be maintained in locked offices or computers with access available only to those individuals directly involved with this study. A generated subject number will identify research subjects. All efforts will be undertaken to ensure patient confidentiality.

13.0 CONSENT/ASSENT

The physicians participating in this study will obtain written informed consent from the adolescent/adult patients and parents/legal guardians after providing a review of the study and the required procedures. Whenever possible, assent will be obtained from children between the ages of 7 and 12 and documented by means of the child's and the physician's signature on the consent form.

14.0 ADVERSE EVENT REPORTING AND DATA SAFETY MONITORING

14.1 Adverse Event Reporting

All patients will have toxicity monitoring for 6-8 weeks following ¹³¹I-MIBG therapy. Toxicities will be graded according to the Common Toxicity Criteria (CTC) version 3.0 (http://ctep.info.nih.gov) and attribution assigned. Toxicities will be summarized and reported annually to the FDA.

All toxicities will be categorized as either expected or unexpected. For the purposes of this trial, all unexpected Grade 4 toxicities and all deaths that occur in the first six weeks following treatment will be categorized as a Serious Adverse Event and will require expedited reporting. All toxic deaths will be reported by phone within 24 hours to the data center at UCSF and the FDA. MedWatch forms will be filed for all unexpected Grade 4 toxicities and deaths with each participating institution's IRB and the FDA. Unexpected Grade 4 toxicities and treatment-related deaths will also be reported in an expedited fashion for patients who remain in "treatment phase" after six weeks (i.e. no additional therapy). However, deaths due to progressive disease will not require expedited reporting after 6 weeks.

Other serious adverse events that are coded as unexpected Grade 2 and 3 toxicities will also be reported in expedited fashion as above. No Grade 1 toxicities will require expedited reporting.

All toxicities will be collected and summarized annually in reports to the IRB and FDA.

Grade 4 blood/bone marrow toxicities are EXPECTED and will not require expedited reporting. In addition, because Grade 3 febrile neutropenia is common, hospitalization for fever and neutropenia will be recorded but will not require expedited reporting. Grade 4 febrile neutropenia (septic shock) or any Grade 4 infection will be reported using the expedited system noted above.

Grade 4 pain due to the patients disease and/or hospitalizations to manage symptoms from the underlying disease will be recorded but not require expedited reporting.

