1.0 SPECIFIC AIMS

Malignant adrenal pheochromocytoma (PHEO) and extra-adrenal pheochromocytoma (paraganglioma, PGL) remain fatal cancers for the majority of patients, with an average survival of 4.5 years. ¹³¹I-metaiodobenzylguanidine (¹³¹I-MIBG) is a norepinephrine analog that concentrates in adrenergic tissue and therefore holds promise for cell-specific treatment of malignant PHEO/PGL. ¹³¹I-MIBG is active against malignant PHEO/PGL. The associated hematopoietic toxicity can be abrogated with autologous stem cell rescue. ¹³¹I-MIBG given in doses of 8-12 mCi/kg with stem cell rescue, if necessary, is a reasonably safe and effective palliative therapy for patients with refractory or relapsed malignant PHEO/PGL.

Primary Aims:

- Provide palliative therapy for patients with malignant PHEO/PGL.
- Gain more information about acute and late toxicity of ¹³¹I-MIBG therapy for patients who have metastatic PHEO/PGL.

Secondary Aim:

• Obtain disease and symptom responses on patients with malignant PHEO/PGL who are not eligible for other therapy of higher priority.

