2.2 UCSF Experience

Fifty-five patients with metastatic PHEO/PGL have been treated with doses of ¹³¹I-MIBG ranging from 492 mCi to 1160 mCi. Prior publications have described our first 12 patients and first 30 patients. We now have response data from the first 50 patients with metastatic PHEO/PGL treated at UCSF with ¹³¹I-MIBG:

Cumulative ¹³¹I-MIBG ranged from 492-3191 mCi. Autologous hematopoeitic stem cells were collected and cryopreserved prior to treatments with ¹³¹I-MIBG in doses >12 mCi/kg or >500 mCi/kg. Thirty-five patients were treated once, while 15 patients received two or three treatments. By RECIST criteria, the overall combined complete response (CR) plus partial response (PR) rate was 22%. Additionally, 35% of patients achieved a CR or PR response in at least one measure of hormonal response, without any progressive disease, and an additional 8% of patients maintained stable disease >12 months. Thirty-five percent of patients experienced progressive disease within one year following therapy. The estimated 5-year overall survival was 64%. Toxicities included: grade 3-4 neutropenia (87%) and thrombocytopenia (83%).

Grade 3-4 non-hematologic toxicity included: pulmonary embolism (n=1), fever with neutropenia (n=7), acute hypertension (n=10), infection (n=2), hypogonadism (n=6).

Two patients developed bronchiolitis obliterans organizing pneumonia (BOOP) after ¹³¹I-MIBG doses of 845 mCi (8.1 mCi/kg) and 1062 mCi (16.9 mCi/kg) respectively; both patients recovered. Two patients developed acute respiratory distress syndrome (ARDS) after ¹³¹I-MIBG doses of 1,160 mCi (18 mCi/kg) and 1,030 mCi (12.1 mCi/kg) respectively. One patient (with a heavy secretory tumor burden and severe nephrotic syndrome) died from ARDS. Two patients developed myelodysplastic syndrome (MDS) with acute myelogenous leukemia after partial remissions lasting 5 and 2 years following ¹³¹I-MIBG at cumulative doses of 1,712 mCi and 1832 mCi respectively.

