- **4.24** Imaging. For all patients, a scintigraphic MIBG imaging study, comparable to the diagnostic scan, will be done near the time of discharge, usually on day 4 or 5 post-treatment. This scan is performed to confirm tumor uptake and also to survey for occult sites of disease. Patients will not receive any MIBG injection for this scan. Some patients may elect to participate in a separate organ or tumor dosimetry study, which would require a separate consent and extra images.
- **4.25** G-CSF. Patients whose ANC is less than 500/uL after MIBG infusion will begin G-CSF 5 mcg/kg/day (or an equivalent single dose of Neulasta) subcutaneously until neutrophil recovery.

4.3 **Post-Treatment Evaluation**

Post-treatment evaluation will be performed 8-12 weeks after treatment. Required studies are detailed in Section 5.0

4.31 Toxicity. Complete FDA Form 3500A (Medwatch) for grade 3 and 4 toxicities except expected hematologic toxicities and fever. Deaths occurring <6 weeks post treatment should be reported.

4.4 Criteria for hematopoietic stem cell infusion.

It is recommended that a patient receive an infusion of a portion of their cryopreserved autologous hematopoeitic stem cells if they develop grade 4 hematologic toxicity following ¹³¹I-MIBG therapy and continue to have an ANC < 200/uL on G-CSF/Neulasta without signs of recovery for > 2 weeks. In addition, any patient requiring platelet transfusions more than two times weekly for 2 consecutive weeks will receive hematopoietic stem cell rescue. Stem cell infusion may occur sooner or later if indicated (i.e. due to an infectious or bleeding complication) after consultation with the Study Chair or designee.

4.5 Criteria for subsequent treatment. Patients may be eligible for additional ¹³¹I-MIBG therapies if they meet the following criteria:

- **4.51** Minimum of eight weeks from previous MIBG therapy on this study.
- **4.52** Response or stable disease after the first infusion. If patient responds with a CR to the first infusion, the patient may receive a second therapy as consolidation.
- **4.52** Meets all other criteria as outlined in eligibility and pre-treatment evaluation sections above except for platelet count. Patient may be thrombocytopenic, but requiring no more than 1 platelet transfusion per week to maintain counts above 20,000.

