7.0 STATISTICAL CONSIDERATIONS

Efficacy

This is a compassionate use protocol to be used as best available therapy for palliation in patients who are not eligible for protocols of higher priority. The endpoints to be analyzed will be progression free survival, survival, response and toxicity. The anticipated accrual is 4 patients per year with a total accrual of approximately 50 patients.

Toxicity

Because this is a group of patients with very far advanced disease, stopping rules will be in place. If there is >1 toxic death in the first 10 patients treated, or >2 in the first 20, then the protocol will be suspended and the data reviewed. All grade 3 and 4 toxicities will be recorded and reviewed every six months. If non-hematologic grade 4 toxicity is seen in >15% of patients, the protocol will be suspended and reviewed.

Sample Size Justification and Accrual

This study will provide additional safety data for FDA approval of MIBG and efficacy data. The FDA is interested in long-term safety and toxicity data, so the accrual of additional patients beyond that of the previous phase II study will allow this goal to be met. It is anticipated that ¹³¹I-MIBG will eventually be approved for commercial use in patients with metastatic pheochromocytoma and paraganglioma, and therefore prolongation of this compassionate use protocol will no longer be necessary.

Safety Analysis

Grade 3 and 4 adverse events will be coded by the NCI Common Toxicity Criteria v3 and summarized. Within each body system, the severity will be summarized, as well as worst toxicity overall for each patient.

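### Late toxicity is a primary aim, but toxicity monitoring is set at 6-8 weeks, and later follow-up is only recommended, stops at progression or other therapy, and specifies no late-event collection

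*Protocol*

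**What the plan says.** **Aim and rationale.** A primary aim in section 1.0 is to "Gain more information about acute and late toxicity of" MIBG therapy. Section 7.0 explains the accrual on the ground that "The FDA is interested in long-term safety and toxicity data".

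**Stated window.** Section 14.1: "All patients will have toxicity monitoring for 6-8 weeks following" MIBG therapy. The same section expedites certain events after six weeks: unexpected Grade 4 toxicities and treatment-related deaths, in patients who have had no additional therapy. It also says that all toxicities are collected and reported annually, without giving an end date.

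**Other time points.** Section 4.3: "Post-treatment evaluation will be performed 8-12 weeks after treatment". The table in section 5.0, which is described as serving toxicity and response monitoring, has a last column of Day 56-120. The only post-treatment thyroid tests in that table are in that column.

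**Longer follow-up.** Section 5.1 is headed as recommended. It lists blood counts, liver tests, thyroid tests and an MIBG scan every 3 months to 1 year and every 6 months after that, until progression, death or other therapy.

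**Known late events.** Section 2.2: "Two patients developed myelodysplastic syndrome (MDS) with acute myelogenous leukemia after partial remissions lasting 5 and 2 years following" treatment. Section 9.0: "Secondary leukemia or other malignancy is also a known but rare (<5%) risk of radiation".

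**The concern.** An aim about late toxicity needs a rule that late events are sought, in whom, and until when. The only period the protocol labels as toxicity monitoring ends at 6-8 weeks, and the follow-up that runs for years is optional and depends on disease status. Patients who progress or start another treatment leave that follow-up, although they remain at risk of late effects of the radiation already received.

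At stake are a primary aim and the stated reason for enrolling about 50 patients. No later analysis can recover events that were never collected, so this cannot be left to a statistical analysis plan.

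**Working it through.** The protocol gives no calculation on this point to reproduce. The check compares the time windows and then sizes the effect of stopping follow-up at progression.

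**1. Windows side by side**

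| Element | Section | Time after treatment |
|---|---|---|
| Toxicity monitoring | 14.1 | 6-8 weeks = day 42-56 |
| Post-treatment evaluation | 4.3 | 8-12 weeks = day 56-84 |
| Last required observations | 5.0 | Day 56-120 (120/7 = 17.1 weeks) |
| Recommended follow-up | 5.1 | To progression, death or other therapy |
| MDS/AML cases | 2.2 | After remissions of 2 and 5 years |

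The 4.3 evaluation and the last 5.0 column start where the 14.1 window ends. Two years is 104.4 weeks and five years is 260.9 weeks, so 104.4/8 = 13 and 260.9/8 = 33 times the 8-week limit.

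**2. What 5.1 could detect.** A patient without progression or other therapy would have 4 + 2 = 6 scheduled blood counts by 2 years and 4 + 8 = 12 by 5 years. Leukemia could be found in such a patient, if the recommended visits take place.

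**3. What 5.1 does not ask for.** It names no second malignancy, gonadal, lung, heart or kidney events. Section 2.2 reports six cases of grade 3-4 hypogonadism and section 9.0 lists infertility in the 5-20% band, yet neither 5.0 nor 5.1 contains a test of gonadal function.

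**4. Person-time lost by stopping at progression (illustration).** Inputs from section 2.2: five-year survival 64%; 35% progressive disease within one year. Assumptions: constant death hazard; 35% leave follow-up in year 1; the later hazard of leaving is a chosen fraction of the year-1 hazard; all patients attend until they leave. Person-years per patient between years 2 and 5 are [S(2) - S(5)]/h, where S is the proportion still followed and h the hazard over that interval.

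- To death: h = -ln(0.64)/5 = 0.0893; S(2) = 0.8365, S(5) = 0.64; (0.8365 - 0.64)/0.0893 = 2.20.
- Stopped at progression, constant hazard: h = -ln(0.65) = 0.431; S(2) = 0.65^2 = 0.4225, S(5) = 0.65^5 = 0.1160; 0.3065/0.431 = 0.71. Loss 1 - 0.71/2.20 = 68%; 11.6% still followed at 5 years.
- Hazard halved after year 1: h = 0.2154; S(2) = 0.65^1.5 = 0.5240, S(5) = 0.65^3 = 0.2746; 0.2494/0.2154 = 1.16. Loss 47%; 27.5% still followed at 5 years.
- Hazard quartered after year 1: h = 0.1077; S(2) = 0.65^1.25 = 0.5836, S(5) = 0.65^2 = 0.4225; 0.1611/0.1077 = 1.50. Loss 32%.

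Stopping at other therapy is not modelled and would add to each loss.

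**5. Scale of the leukemia risk.** Section 2.2 gives response data on 50 patients and 55 treated. 2/50 = 4.0% (exact 95% interval 0.5% to 13.7%); 2/55 = 3.6% (0.4% to 12.5%). If the true risk were 4% and long-term follow-up complete, 50 patients would give 1 - 0.96^50 = 87% chance of at least one case.

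**The case against.** The protocol does look beyond 8 weeks. Section 5.0 requires toxicity observations to Day 120, and 5.1 recommends blood counts for years. Section 14.1 collects all toxicities annually, and sections 7.0 and 14.2 provide six-monthly toxicity reviews, none with an end date. Survival is an endpoint (7.0) and time to death is to be evaluated (3.0), so some contact after progression is implied. The aim is only to gain more information, with no target precision, in a descriptive compassionate-use study.

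Most of this stands, and it rules out stronger readings that a reader might infer:

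- *The leukemias at 2 and 5 years fall outside the plan.* They fall outside the 14.1 window. If the remissions lasted until diagnosis, both patients would still have been within 5.1 follow-up; the text does not say whether they did.
- *Leukemia escapes because it is an expected event.* The protocol does not define expected events by the risk list in 9.0, and the sentence about the period after six weeks governs expedited reporting, not collection.
- *The risk will be understated by a crude count over 50.* No section plans that estimator, and the choice of method can be left to the statistical analysis plan.

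The loss figures also depend on assumed hazards after year 1, and lost person-time is not the same as lost events.

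The objection does not remove the gap. An annual report or a six-monthly review can contain only what was sought, and nothing requires late events to be sought after Day 120 or in any patient who has progressed or changed therapy.

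**Conclusion.** The point holds in this limited form: the sections on aim, schedule and adverse events disagree, and the plan does not secure the late-toxicity data that it names as a primary aim and as its reason for accrual. Late events would be captured incompletely, because follow-up past Day 120 is optional and has no event list, and selectively, because it retains patients whose disease is controlled and who have had no other therapy.

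The losses of 68% and 47% of person-time between years 2 and 5 are illustrations, not bounds. They rest on the 35% and 64% in section 2.2 carrying over to this trial and on a constant or halved hazard after year 1; at a quarter of the hazard the loss is 32%. It would go too far to say that the trial cannot answer its aim: 5.1 would yield some late data. It is not set up to do so reliably.

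**What to change.** Amend the protocol so that sections 1.0, 4.3, 5.0/5.1, 7.0 and 14.1 agree:

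- In 14.1, label the 6-8 week window as acute toxicity, and reconcile it with the 8-12 week evaluation and the Day 56-120 observations.
- Require late-toxicity collection at the 5.1 visits and afterwards with the survival follow-up, regardless of progression or new therapy. At a minimum, record MDS/AML, second cancer, persistent cytopenia, thyroid and gonadal failure, and cause of death.
- Record any intervening anti-tumor therapy and its dates.

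The analysis method for late events can be specified in the statistical analysis plan. The change alters data collection, not treatment.

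The cost is an amendment, a short form and periodic contact, much of which the survival endpoint already implies. The drawback is that events after other therapy are harder to attribute, which is why the intervening treatment must be recorded.
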